1.0 Study Summary

Study Title	Testing a Low Cost Population- and Theory-Based Outreach Intervention to Engage Ovarian Cancer Survivors and their Close Relatives to Consider Genetic Services
Study Design	randomized intervention trial
Primary Objective	
Aim 1: To enlist community partners as citizen scientists to: identify and recruit Georgia residents with a personal/family history of ovarian cancer, generate content, and collaborate on a scalable message-based outreach intervention to reach ovarian cancer survivors and close relatives (i.e., first- and second-degree relatives) to consider genetic service options.
 
Aim 2: In a two-arm randomized intervention trial (RCT), to compare a message-based outreach intervention to standard outreach for effects on: survivor reach, relative reach, and uptake of appropriate cancer genetic services (i.e., genetic counseling and testing for survivors, online genetic risk assessment for relatives) among survivors of ovarian cancer identified via a state cancer registry. We hypothesize that the message-based approach will result in greater reach and uptake of genetic services than standard outreach.
 
Aim 3: To conduct a process evaluation consistent with the RE-AIM framework alongside the RCT to measure: reactions, dose delivered/received, fidelity, acceptability, barriers/facilitators, and alignment with ethical principles.

Secondary Objective(s)	N/A
Research Intervention(s)/Interactions	A message-based outreach intervention
Study Population	Georgia residents with a personal or family history of ovarian cancer
Sample Size	1,240
Study Duration for individual participants	
Study duration varies for different participants.
 
Aim 1 (community working groups): Eligible participants are: English-speaking, have a personal

	
and/or family history of ovarian cancer, 25 years or older, have access to the internet and be available to attend in-person or online focus group discussions. Participants will attend 2 to 3 90-minute in-person meetings and some additional outside “homework”.
 
Aim 2 (message-based intervention (MBI) and waitlist standard outreach approaches): Eligible survivors are: diagnosed with ovarian, fallopian tube, or peritoneal cancers, lived in Georgia at the time of diagnosis, not deceased, and have a mailing address per the Georgia Cancer Registry (GCR)’s records. Study duration could be up to one year.
 
Aim 2 & 3 (post-intervention online survey): Survivors and relatives in both arms who login to the study website will be invited to complete an one-time online survey. Study duration could be up to 30 min.
 
Aim 3 (mail survey to survivors who did not login to the study website): GCR will send a brief survey with a \$10 incentive to survivors who do not visit the website after the third and final mailing. Study duration could be up to 10 min.
 
Aim 3 (online discussion forum): We propose to purposefully sample survivors (~25) and relatives (~25) randomized to the MBI arm to participate in an online discussion forum. Study duration could be up to 1 hour.
 
Aim 3 (re-engagement of working groups, Year 4): After data analysis is complete (late Year 4), we will reengage community working groups from Aim 1 for a half-day workshop where we will report findings of the intervention and enlist additional feedback.

Study Specific Abbreviations/ Definitions	Georgia Cancer Registry (GCR); Randomized control trial (RCT); Community advisory boards (CABs)
Funding Source (if any)	National Cancer Institute, pending council review

2.0 Objectives*

2.1 Aim 1: To enlist community partners as citizen scientists to: identify and recruit Georgia residents with a personal/family history of ovarian cancer, generate content, and collaborate on a scalable message-based outreach intervention to reach ovarian cancer survivors and close relatives (i.e., first- and second-degree relatives) to consider genetic service options.

Aim 2: In a two-arm randomized intervention trial (RCT, N~2,918), to compare a message-based outreach intervention to standard outreach for effects on: survivor reach, relative reach, and uptake of appropriate cancer genetic services (i.e., genetic counseling and testing for survivors, online genetic risk assessment for relatives) among survivors of ovarian cancer identified via a state cancer registry.

Aim 3: To conduct a process evaluation consistent with the RE-AIM framework alongside the RCT to measure: reactions, dose delivered/received, fidelity, acceptability, barriers/facilitators, and alignment with ethical principles.

2.2 We hypothesize that the message-based approach will result in greater reach and uptake of genetic services than standard outreach.

3.0 **Background***

The majority of women at greatest risk for ovarian cancer due to hereditary factors are unlikely to know about their elevated risk and prevention opportunities. This significant gap in outreach means that most at-risk women will receive a late diagnosis of ovarian cancer with a dramatic negative effect on survival.¹ Traceback approaches that leverage state-wide cancer registries' ongoing surveillance activities offer a potentially low cost platform for outreach to ovarian cancer survivors and their close relatives.

Approximately 15-20% of epithelial ovarian cancers are due to inherited mutations in cancer predisposing genes.² As such, it is now routine in specialty cancer care settings to offer genetic counseling and testing to all patients diagnosed with ovarian cancer.^{3,4} To promote cascade testing, patients identified with deleterious mutations are generally sent notification letters, and informational materials for specific relatives recommending that relatives seek genetic counseling. The sensitivity of a survivor's mutation status supports the prevailing notion that only the survivor should directly contact close relatives. The few rigorous evaluations of these approaches consistently show limited reach both to survivors and their relatives particularly for rural residents, relatives with low income, and racial minorities.⁵⁻⁷ Current specialty-clinic-centric approaches, despite efforts to expand reach, are not achieving the objective to ensure that all groups benefit from increasing knowledge about hereditary cancer.

An essential function of public health is to ensure the broad reach of prevention programs (e.g., reaching tobacco users to offer cessation programs). However, health professionals have yet to apply much of the three-decades of evidence gained by these programs to promote health among people affected by hereditary cancers. Research shows that multi-component, low cost health communication interventions including foot-in-the-door techniques,⁸ tailored/targeted communications,⁹ website support,^{10,11} and short messages¹² expand reach of prevention messages. Moreover, guidance from

theory is critically important to effective cancer communications as fatalistic beliefs about prevention and survival are common.¹³⁻¹⁵ Health professionals must anticipate the potential for motivated processing of ovarian cancer risk information—denial, counter-arguing or avoidance—that can undermine engagement among those who are reached by traceback programs and the uptake of genetic services. Theory-based interventions offer strategies to counter these responses and suggest that interventionists must develop specific messages in collaboration with affected communities.¹⁶⁻¹⁸

The shift from clinic-based promotion of cascade testing to population-level traceback programs introduces a number of ethical questions. The current prevailing notion that the patient must make the initial contact with close relatives warrants reconsideration. Indeed, no systematic efforts have assessed close relatives' preferences regarding direct contact, especially in the circumstances where the patient's mutation status is unknown. Citizen science methods offer a low cost and feasible platform for gaining community wisdom and creativity related to the ethical challenges of population outreach.

With the availability of life-saving prevention options, we need novel approaches to identify, engage and inform ovarian cancer survivors and their close relatives about their risk. State cancer registries are a viable platform to use low cost outreach approaches to contact survivors, offer genetic counseling and testing as well as options for contacting relatives.^{1,19,20}

4.0 Study Endpoints*

4.1 Primary RCT outcomes: 1) Survivor reach: the proportion of the eligible survivors identified and contacted by GCR who log in to the website, 2) Close relative reach: the proportion of close relatives enumerated by survivors who log in to the website, and 3) Uptake of cancer genetic services: the proportion of untested survivors who complete telegenetic counseling and the proportion of relatives enumerated who complete B-RSTTM screening and subsequently access genetic counseling. We will evaluate secondary outcomes: In the MBI arm, we will track survivor' and relatives' patterns of website usage including: duration of time on the website, number of return visits, pages viewed, and the proportion of survivors who select different relative contact options.

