A.3. Working Group Procedures: [name] who has experience working with community groups and evaluating websites that link those with inherited disease to genetic services will oversee working group activities.²⁵ In *iteration 1*, one community working group will recommend approaches for framing the “large ask” and choice sets for relative contact options. A second and third working group will assist in collecting survivor-family stories using photonovela or other strategies. In *iteration 2*, content experts in communication, genetics and ethics will assemble working group content and develop initial formats for the website and print materials. Communication and bioethics experts will review materials for alignment with communication frameworks and ethical principles. Next, Peachtree Solutions (see letter of support), our web-development partner, will work with Emory’s Visual Medical Education team to draft the website and print materials. In *iteration 3*, a third community working group will review initial and revised iterations of intervention content using systematic cognitive interviewing methods.²⁶ Peachtree Solutions has extensive experience with the latest usability standards and will direct the usability testing. The investigative team and consultants will make revisions based on each round of panel input. We will use the Suitability Assessment of Materials (SAM) and Comprehensibility (CAM) scale to evaluate the readability and comprehensibility of the website with the aim to develop a website that users’ rate as “superior”, indicating it is easy to use and understand, low in cognitive demand, attention-getting, and motivating.²⁷

Prior to fielding the trial, we will submit the developed study materials as part of IRB amendment.

[figure not shown]
B. Aim 2: Conduct a two-arm randomized intervention trial (N~2,918).

B.1. Study Design: We will compare the message-based intervention (MBI) developed in Aim 1 to standard outreach in a two-arm RCT in Years 2 and 3. The MBI comprises a combination of novel intervention components that depart sufficiently from prior research to warrant a comparison arm (with access to the MBI website when the trial period is completed).²⁸ Figure 2 displays the flow of the intervention.

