B.5.1.a. Website: The study website developed in Aim 1 will be a centralized information delivery portal that contains: graphical depictions of genetic risk, short videos on hereditary cancer risk, photonovelas, structured interactive Q&A choices highlighting pros and cons of seeking genetic services from the perspectives of survivors, and resources for patient navigation programs near them. On entering the website, survivors will see an explanation of the study and the opportunity to continue or to decline. The online consent form ends with the "I agree" checkbox so the participant can decide whether they still want to participate after reading the listed conditions. [name] successfully used a similar approach with 6,400 enrollees in a managed care organization.⁵⁴ Fully 32% of those who received mailed invitations with log-in information visited the website.⁵⁵ Results showed high levels of information recall and accurate interpretations of the limits of the genetic susceptibility testing for common diseases suggesting this platform enabled informed consent.⁵⁶ The website will ask survivors who log-in to review informed consent information, click the "I agree" button if they want to proceed, and on a separate webpage to complete the requested "*small ask*" task to enumerate their 1st and 2nd-degree relatives (henceforth "close relatives") by first name only and to specify the relationship. Once completed, the survivor will view options for how close relatives might be contacted (we will present 3-4 options that represent graduated involvement of study staff). We will pair each option with personal stories to illustrate pros and cons of the choices. The website will then prompt survivors to complete the "*large ask*" task, which entails selecting an option (e.g., close relatives contacted solely by survivor, share contact of some relatives with study team, study team contact all enumerated relatives, refuse contact, etc.). Survivors who select options that involve the study team reaching out on the survivor's behalf will be prompted to provide contact information (e.g., mailing address, email, phone number) for relatives. Relatives specified for study contact will be sent (via email, mail or text) personal login information linked to the survivor; provide survivors

Figure 3: MBI flow of survivor-relative contact

Survivor receives packet/website login from GCR

"Small ask task"-Login to website and enumerate relatives

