- Relative 1: first name, relationship
- Relative 2: first name, relationship
- ...etc

"Large ask task"-Select contact choice for enumerated relatives

- Relative 1: first name, relationship

A. Select willingness to contact:

- Yes, no, will decide later

B. If yes, select contact method:

- Survivor contact only
- Study team contact only
- Survivor and study team
- Other choices developed in Aim 1

C. If agree study team contact, provide relative contact information:

- Mail, email, or phone number
- Relative 2:
- ...etc

Relative receive unique website login depends on contact choice

who opt to contact relatives will be provided with unique log-in information for each of the relatives they list. Relatives that survivors refuse contact will be noted but not contacted.

B.5.1.b. Short messages: Survivors who provide mobile phone numbers will receive two SMS thanking them for accessing the website, and encouraging them to revisit the website to review information and contact relatives. We will time these cues to occur at 3-week intervals over a 6-week time period (two SMS). Additionally, reviews of SMS studies suggest including a substantial pre-testing phase that allows target audiences to provide input on message content as we propose to do in Aim 1.

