
B.5.2. Close relative procedures: Relatives eligible to participate must be: 25 years or older (age recommended to initiate preventive behaviors)⁶⁰, able to access the internet, a 1st or 2nd degree relative of the survivor, able to read English, and non-incarcerated or institutionalized. Relatives will receive a unique website login linked to the survivor that enables access to the website content and describes pros/cons of family-history-based genetic risk screening for HBOC. Additionally, relatives for whom we have cell phone numbers will receive 3 cueing SMS reminders over 9 weeks (developed during Aim 1). The SMS will thank them for visiting the website and

suggest they return as needed and complete the genetic risk assessment for ovarian cancer family history. We will use the B-RST™ (developed and validated by [name] in 2009),^{61,62} which is endorsed by the USPSTF as one of several validated screening tools that is clinically useful for estimating the probability of *BRCA1/2* mutation and identifying women for referral to genetic counseling. This screener assesses personal and family history (1st and 2nd relatives) of breast cancer, bilateral breast cancer, ovarian cancer and male breast cancer, and Ashkenazi Jewish heritage. The intervention website will include a separate portal dedicated to the B-RST™ 3.1 screen. Although all 1st or 2nd degree relatives of ovarian cancer survivors will screen positive on B-RST™, completing the screener will raise participant awareness of the factors that contribute to hereditary risk of ovarian cancer and will reinforce the salience of seeking genetic counseling. We will recommend genetic counseling for all close relatives because of their heightened risk for carrying a *BRCA1/2* mutation. We will direct interested relatives to the same telegenetic counseling services provided to survivors. Ideally, we would recommend testing the survivors first, and only offer genetic testing to close relatives with a confirmed pathogenic variant ala cascade testing. However, we will offer genetic testing to relatives regardless of survivor's testing status.

B.6. Standard Outreach Arm

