B.6.1. Survivor components: GCR will mail survivors a standard letter and log-in information. Survivors will have access to a condensed version of the website that includes information on: genetic risk and genetic counseling, patient navigators in their locale, and the importance of conveying information to close relatives. Survivors will be provided with 2 extra letters and login information for 2 close relatives. Survivors can request additional relative letters/logins for any relatives that they would like to involve on the website or the GCR.

B.6.2. Close relative components: The standard family letter shared by the survivor will provide login codes for the relative to visit the condensed website with information about genetic risk and the value of completing the online B-RST™ screener.

All survivors and relatives in the standard arm will have access to the telegenetic counseling services described above. After completion of intervention trial, all survivors in the standard outreach arm regardless of their study participation will have access to the MBI sections of the website.

6.2 *Procedures being performed to monitor participants for safety or minimize risks.*

We expect the research-related risk to be minimal: the probability & magnitude of harm/discomfort anticipated in the research is no greater than those ordinarily encountered in daily life or during the performance of routine physical or psychological examinations/tests.

There are no anticipated physical risks of participating in this study. However, participants may experience psychological or emotional distress from participating in the study, particularly activities related to the way their family interacts or communicates about ovarian cancer and genetic risks. Survivors may worry about their family members' emotional distress. Participants whose motivations for study

enrollment include histories of ovarian cancer in either themselves or their family members may find it upsetting to re-visit their personal experiences.

There is a small potential risk of outreach to family members of a recently deceased woman. In GCR's past experiences, this event does indeed happen on occasion but the typical response is a family member contacts GCR to inform about the passing of their family member. No adverse event has been reported thus far (e.g., distress, confusion). The proposed research activities present the same outreach risk (which is minimal) as routine contact by the GCR.

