Aim 2 (message-based intervention (MBI) and waitlist standard outreach approaches): Ovarian cancer survivors in the Georgia Cancer Registry (GCR) database who meet the following criteria will be considered for study participation: 1) diagnosed with ovarian, fallopian tube, or peritoneal cancers; 2) lived in Georgia at the time of diagnosis; 3) currently are alive per the registry's records; and 4) have a mailing address. The proposed recruitment procedures comply with GCR's current standards and are adapted from strategies that were effective in other studies using cancer registry for recruitment.¹⁻⁵ We will classify survivors who log in to the study website as recruited. Recruitment will rely on multiple communications aimed to encourage survivors to log in to the study website; the number of contacts will be largely identical for both arms: first mail-out (full packet plus \$10 incentive), telephone contact from a trained GCR staff, second mail-out (postcard reminder), and third mail-out (full packet). Our review of registry files as of May 2019 showed that: of the 8,760 women with a diagnosis of ovarian, fallopian tube, or peritoneal cancer (excluding those who were deceased or lost to follow as of 2017), we will have addresses for about 2,918 survivors over the 16-month recruitment period. In a recent study using GCR to recruit breast cancer survivors in Georgia with registry standard mailing and phone contact without financial compensation, 63% agreed to participate.⁶ A conservative assumption of reaching (i.e., log in to the study website) 45% in the MBI arm versus 10% in the standard outreach arm, we need to recruit 801 cancer survivors into our study. Relatives of survivors eligible to participate must be: 25 years or older, have access to the internet, be a first- or second-degree relative of the survivor, able to read English, and not be incarcerated or institutionalized. We estimate that 801 cancer survivors will log in to the website and 75% of them (N=601) will enumerate a median of 2 at-risk relatives. We assume the number of at-risk relatives enumerated will not differ between intervention arms. Furthermore, we estimate that 40% of relatives referred by MBI arm participants will log on compared to 20% in the standard outreach arm. We expect that about 438 relatives will participate in the study. Recruitment of survivors and relatives for the intervention will occur in Year 2 and 3.

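### Relative reach and uptake are compared on a denominator formed after survivor login (planned at 45% vs 10%), with no analysis on all randomised survivors, and relative uptake is defined in three different ways

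*Combined protocol and SAP*

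**What the plan says.** Sections 4.1 and 6.4 define relative reach as "the proportion of close relatives enumerated by survivors who log in to the website". They define relative uptake as the share of enumerated relatives who complete B-RST and afterwards access genetic counselling. Both are listed as primary.

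In the MBI arm, enumeration is a website task that follows login and consent (B.5.1.a). For the standard arm, B.6.1 says "Survivors will be provided with 2 extra letters and login information for 2 close relatives", with more on request, and describes no enumeration step. Section 13.0 plans one count across both arms: of the survivors who log in, "75% of them (N=601) will enumerate a median of 2 at-risk relatives". It adds: "We assume the number of at-risk relatives enumerated will not differ between intervention arms".

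Section 17.0 analyses relative outcomes with a multilevel logistic model, relatives nested in survivors. No relative outcome is analysed on all randomised survivors.

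Relative uptake appears in three forms:
- Aim 2 (sections 1.0 and 2.1): online genetic risk assessment, with no counselling step.
- Sections 4.1 and 6.4: B-RST and then counselling, among relatives enumerated.
- Table 3: B-RST alone, among relatives who logged in (394 vs 44).

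The power text in 17.0 counts four primary outcomes. The analysis text lists five: survivor reach, survivor counselling, relative reach, relative B-RST and relative counselling.

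**The concern.** Randomisation balances survivors, not the relatives whom survivors later list. If the MBI brings many more survivors to the website, its relatives come from a different mix of survivors: those who would have logged in anyway, plus a larger group who log in only because of the MBI. If the relatives of the added survivors are more or less responsive, relative reach will differ between arms even when the MBI changes no relative's behaviour, and the bias can go either way. The multilevel model handles correlation within families; it does not handle this selection. Coding non-engagers as 0 works for survivors but cannot cover relatives who were never listed.

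The three forms of uptake raise a second problem. The power shown in Table 3 is not for the outcome that section 4.1 defines, and an analyst could choose among the forms after seeing data.

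**Working it through.** **Inputs.** 1,459 survivors per arm (B.3). Login 45% vs 10%, relative login 40% vs 20%, B-RST among relatives logged in 70% vs 30%, design effect (DEFF) 1.3 with 2 as a sensitivity value (17.0, Table 3). 75% of logged-in survivors enumerate, median 2, used here as a mean (13.0). No alpha is stated; two-sided .05 is assumed. Power is by normal approximation with pooled variance, each n divided by DEFF.

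**Step 1: reproduce Table 3.**
- Enumerated: 1,459 x .45 x .75 x 2 = 984.8 (985); 1,459 x .10 x .75 x 2 = 218.9 (219).
- Logged in: 985 x .40 = 394; 219 x .20 = 43.8 (44).
- Power for reach: above .99 at DEFF 1.3, .99 at DEFF 2. Power for the B-RST row: above .99 and .97.

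Table 3 reproduces. The uptake row therefore uses relatives who logged in, and both relative rows depend on survivor login.

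**Step 2: size of the selection.** At least (.45 - .10)/.45 = 78% of MBI survivors who log in (656 - 145 = 511 of 656) would not have done so under standard outreach.

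**Step 3: what it could do.** The documents give no figure for how the relatives of these two groups differ, so the response rates below are assumptions. All control-arm loggers are assumed also to log in under the MBI, and the MBI has no effect on any relative. MBI reach = (.10 x r + .35 x q)/.45, where r is response among relatives of survivors who would log in under either arm and q is response among relatives of added survivors. Control reach = r.

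| r | q | MBI reach | Control reach | False rejection, DEFF 1.3 | DEFF 2 |
|---|---|---|---|---|---|
| 20% | 25% | 23.9% | 20% | .18 | .13 |
| 20% | 15% | 16.1% | 20% | .24 | .18 |
| 20% | 10% | 12.2% | 20% | .73 | .57 |
| 40% | 20% | 24.4% | 40% | .98 | .89 |
| 20% | 40% | 35.6% | 20% | .99 | .91 |

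**Step 4: uptake on section 4.1's terms.** B-RST alone among relatives enumerated is .40 x .70 = 28% vs .20 x .30 = 6% of 985 vs 219. Power is above .99 at both design effects. The full outcome also needs a counselling rate g after B-RST, assumed equal in both arms, giving .28g vs .06g:

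| g | Power, DEFF 1.3 | DEFF 2 |
|---|---|---|
| 68% | >.99 | >.99 |
| 50% | >.99 | .97 |
| 30% | .94 | .76 |
| 20% | .76 | .49 |
| 10% | .34 | .18 |

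Fisher exact to likelihood-ratio calculations at g = 20% give .78 to .86 (DEFF 1.3) and .52 to .68 (DEFF 2).

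The 68% is inferred from section 6.4, where about 70 sessions are 10% of the total, so about 700. Survivors account for 656 x .70 + 145 x .30 = 503, leaving 197. B-RST completers number 394 x .70 + 44 x .30 = 289, and 197/289 = 68%. Sessions are not split by type, and post-test sessions would lower this, so it is an upper figure.

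**Step 5: per randomised survivor (at least one relative).** With both listed relatives behaving alike: login .45 x .75 x .40 = 13.5% vs .10 x .75 x .20 = 1.5%; B-RST .3375 x .28 = 9.5% vs .075 x .06 = 0.45%. With independent relatives: 21.6% vs 2.7% and 16.3% vs 0.87%. Power on 1,459 per arm is above .99 in every case, also at alpha .01 (.05 divided by five outcomes).

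**The case against.** The strongest reply has four parts.

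First, the plan does tie the control count to login and enumeration. Section 13.0 applies the 75% and the median of 2 to survivors in both arms, Table 3 carries 219, and section 6.4 lists enumeration of relatives as website data without limiting it to one arm. This stands. A reader might infer that the standard arm has no denominator at all; the documents do not support that. What the text lacks is the standard-arm procedure. The flow chart ("Figure 2 displays the flow of the intervention") is not shown in the text reviewed and may supply it. Similarly, first-name listing and relatives for whom contact is refused leave detail to be filled in, but on a literal reading a listed relative counts.

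Second, Table 3's numerator agrees with Aim 2. This also stands: section 4.1 is at odds with the Aim as much as Table 3 is with section 4.1, and either could be changed.

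Third, a reader might infer that relative uptake is underpowered. That does not follow. B-RST alone keeps power above .99 on the enumerated denominator, and the session count is compatible with a counselling rate at which the composite does too. Power is unstated rather than shown to be low.

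Fourth, the twofold response gap is an extreme. Gaps of five percentage points give .18 to .24 at DEFF 1.3. That is fair, and the range should be read as a whole; even its lower end is well above .05.

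**Conclusion.** The point holds on two counts. The comparison of relative proportions rests on a denominator formed after randomisation and tied to login at 45% vs 10%, and 17.0 offers no relative analysis that randomisation protects. The 78% follows from the planned login rates alone. The false-rejection range, about .18 to .98 at DEFF 1.3, rests on assumed differences in relatives' response and would be nil if the two groups of relatives responded alike. It would be too strong to say that the relative results will be biased, or in which direction. Survivor reach, analysed on all 1,459 per arm, is unaffected.

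Secondly, Aim 2, sections 4.1 and 6.4, and Table 3 disagree on relative uptake, and 17.0 disagrees with itself on four or five primary outcomes. Table 3's arithmetic is correct; its stated power above .99 simply does not refer to section 4.1's outcome. Because primary outcomes are involved, both matters should be settled before any arm-level result is seen.

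**What to change.** 1. Add to 17.0 a logistic regression per randomised survivor (1,459 per arm) of at least one relative logging in and at least one relative completing B-RST, as the randomisation-protected comparison. State its status among the primary outcomes. If the counselling composite is kept, analyse it the same way with a Firth-penalised or exact method, since control events may be very few.
2. Keep the planned proportions, labelled as conditional on survivor login and enumeration, and show survivor reach beside them.
3. Reconcile Aim 2, 4.1, 6.4, Table 3 and the analysis text on one relative-uptake outcome, one denominator and one number of primary outcomes. If section 4.1's composite stays, restate the Table 3 row with the relative counselling rate as an explicit assumption. At the same time, state how the standard-arm count is formed.

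The cost is wording, one table row and a small extra analysis. It requires that standard-arm relative logins be linked to the survivor; section 22.0 says relatives' logins are linked, without naming an arm. Section 13.0 refers to prior recruitment data and January 2023, so if recruitment has begun, record that the change was made without sight of results by arm.

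The downside is that the per-survivor outcome mixes survivor reach with relative response. If relative response under the MBI were half that of control (10% vs 20%, relatives in pairs), it would still show .3375 x .10 = 3.4% vs 1.5%, favouring the MBI with power about .91. It therefore supplements the conditional proportions and cannot replace them.
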